This is a retrospective controlled survey-study to assess the safety of treating migraine with Nerivio during pregnancy and 3 months postpartum. We will compare migraine and pregnancy related health and baby health between women with migraine who treated migraine attacks during pregnancy with Nerivio (Nerivio group), to women with migraine who did not treat migraine attacks during pregnancy with Nerivio (control group). Nerivio group participants will be recruited from Theranica's user base. Control group participants will be recruited by health care providers, including headache specialists and OBGYNs (study co-investigators). The study is fully electronic, including an e-eligibility questionnaire, an e-ICF, and an e-survey. Participants will be compensated for their time.

Goal

Assess the safety of treating migraine with Nerivio during pregnancy and 3 months postpartum.

Study Design

Retrospective controlled survey-study.

Study group: Postpartum patients with migraine who used Nerivio at least 3 times during their "study pregnancy"

Control group: Postpartum patients with migraine who did not use Nerivio during their "study pregnancy"

Eligibility

Inclusion criteria:

- 1. Diagnosed with migraine
- 2. History of migraine pre-pregnancy with an average of at least 4 migraine days per month, in the six months prior to the last pregnancy
- History of pregnancy with last menstrual period (LMP) between November 1st, 2019 –
 March 31st, 2021. Pregnancy within this time window is the pregnancy of study, termed
 "study pregnancy"
- 4. Between 18 and 42 years of age at first day of the last menstrual period (LMP) of "study pregnancy"
- 5. History of at least 4 migraine attacks during "study pregnancy"
- 6. In the study group: usage of Nerivio for at least 3 treatments (≥30 minutes/treatment) during "study pregnancy"
- 7. In the control group: No history of using Nerivio, ever

TCH-011 Clinical Study Protocol

Doc ID: TECXXXX

Revision #: 1.0

Page: 5 of 25

Exclusion criteria:

- 1. History of preterm birth (gestational age at deliver<37 weeks) in previous pregnancies prior to the "study pregnancy"
- 2. History of congenital malformations or birth defects in previous pregnancies prior to the "study pregnancy"

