- 3. Severe other diseases which started before the "study pregnancy" and lasted into the "study pregnancy" period, including congenital heart disease, arrhythmia, history of myocardial infarction (MI), history of stroke, or active cancer
- 4. Serious physical injury that occurred during the "study pregnancy": severe car collision injury, serious injury at home/work, etc. Multiple gestation (i.e., pregnancy with more than one baby at a time, such as pregnancy with twins, triplets, and quadruplets) in the "study pregnancy"

Study Design and Recruitment

Study group: Study group participants will be recruited from Nerivio's user base. An invitation message will be sent via in-app notification and/or email to all Nerivio users who are (1) female, AND (2) between 18 and 42 years of age as of November 1st, 2019 - March 31st, 2021. Users who meet these criteria will be invited to fill in a screening and eligibility questionnaire. If they meet the eligibility criteria, they will be offered the opportunity to participate in the study. Participants will complete and sign an electronic informed consent form. Following consent, participants will be asked to complete the questionnaire. Once complete, participants will be compensated for their time.

Control group: Control group participants will be referred to the study by site co-investigators, who are US licensed healthcare providers seeing women with headache disorders and/or women during their pre-pregnancy and/or pregnancy period. Patients interested in participating will be directed to the same screening and eligibility questionnaire and will follow the same study design.

Endpoints

Endpoints focus on the health of the mother and the baby, during pregnancy and three months postpartum.

Primary endpoint:

Demonstrate that the study group is not different than the control group in regard to gestational age at delivery (measured in pregnancy weeks).

QMS document

TCH-011 Clinical Study Protocol

Doc ID: TECXXXX

Revision #: 1.0

Page: 6 of 25

Secondary endpoints:

Demonstrate that the study group is not different from the control group in:

- 1. Baby's birth weight (average birth weight)
- 2. Miscarriage rate (% of miscarriage cases)
- 3. Preterm birth rate (% cases of preterm pregnancies, as measured in % of pregnancy weeks less than 37)
- 4. Birth deficits rate (% of birth deficits)
- 5. Still births rate (% of still births)

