- 6. Meeting developmental milestones following 3 months postnatal (% of babies)
- 7. Visits to the emergency room or urgent care due to pregnancy and/or migraine symptoms during pregnancy and 3 months postpartum period (# of events)

Exploratory endpoints: Difference between the study group and the control group in:

- 1. Overall subjective **feeling of safety** using acute migraine treatments during pregnancy (in subjects who used such treatments).
- 2. Overall subjective **satisfaction** with the acute migraine therapies used during the pregnancy (in subjects who used such treatments).
- 3. APGAR score at 5 minutes.

Data analysis

Statistical Hypothesis

The goal of the proposed study is to test the null hypothesis that treating with Nerivio during pregnancy does not impose a safety risk relative to standard care migraine treatment for pregnant women. In other words, the hypothesis is that the means of the two populations are equal. Thus, in this study, the following hypotheses will be tested:

• Null hypothesis: H0: GAt = GAc

• Alternate hypothesis: H1: GAt ≠ GAc

Where GAt and GAc are the average Gestational Age in the study group and control group, respectively. If the null hypothesis is not rejected, the study will be deemed successful. The criterion for significance has been set at 0.05. The test is 2-tailed.

TCH-011 Clinical Study Protocol

Doc ID: TECXXXX

Revision #: 1.0

Page: 7 of 25

Planned Sample Size

Based on USA data from 2020 [Osterman M, et al. Births: Final Data for 2020. Natl Vital Stat Rep. 2021] we assume mean gestational age (GA) of 38.4 with standard deviation of 2.7 (range 26-42).

With the proposed sample size of 114 for each group, the study will have power of 80% to yield a statistically significant result. This computation assumes that the mean difference is less than 1.0 week, and the common within-group standard deviation is 2.7. This effect was selected as the smallest effect that would be important to detect.

Precision for estimating the effect size: We further estimate the mean difference between the two populations. On average, a study of this design would enable us to report the mean difference with a precision (95% confidence level) of plus/minus 0.70 weeks.

Given this statistical requirement up to 400 participants will be recruited per group.

Statistical Analysis Plan

Data will be collected from all patients recruited to the study. Data analysis will not include patients who are:

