- 10. Were you seriously injured during your "study pregnancy", e.g., had a car accident, work injury, home accident, assault, etc.?
 - Yes

TCH-011 Clinical Study Protocol

Doc ID: TECXXXX

Revision #: 1.0

Page: 10 of 25

No

Yes = not eligible

- 11. Do you have a history of preterm birth (delivery at gestational age under 37 weeks) with any of your previous pregnancies (before the "study pregnancy")?
 - Yes
 - No

Yes = not eligible

- 12. Do you have a history of congenital malformations or birth defects in any of your previous pregnancies (before the "study pregnancy")?
 - Yes
 - No

Yes = not eligible

Eligibility messages:

Not eligible message: Message presented to subjects if they do **not meet** the eligibility criteria as identified during the screening questionnaire:

Thank you for your interest in the study on migraine treatments during pregnancy. However, the information you provided indicates that you do not meet the study eligibility requirements, and therefore cannot participate in this survey study.

Eligible message: Message presented to subjects upon the completion of the screening questionnaire, if they **meet** the eligibility criteria as identified during the screening questionnaire:

Thank you for your interest in the study on migraine treatments during pregnancy.

The information you provided indicates that you are eligible to participate in this survey study.

You will now be directed to an electronic informed consent form. Please read the consent form carefully. If you consent, please provide your details and electronic signature at the bottom of the consent form.

Once signed, you will be directed to the survey study questionnaire.

The questionnaire contains 52 questions. It should take approximately 30-40 min to complete the questionnaire.

In order to make it easier and faster to answer the survey questions, we recommend you prepare documents you received upon hospital discharge following delivery of your "study pregnancy", prior to answering the questionnaire.

Please select your referral clinic:

QMS document

TCH-011 Clinical Study Protocol

Doc ID: TECXXXX
Revision #: 1.0

Page: 11 of 25

- 1. Clinic A
- 2. Clinic B
- 3. Clinic C
- 4. Clinic D
- 5. Clinic E
- 6. Other

Single choice

Present the matching ICF, based on participant's clinic

QMS document

TCH-011 Clinical Study Protocol

Doc ID: TECXXXX

Revision #: 1.0

Page: 12 of 25

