TCH-011 Clinical Study Protocol

Doc ID: TECXXXX

Revision #: 1.0

Page: 22 of 25

- Other devices (e.g., gammaCore[™], Cefaly[®], Relivion[®])
- Zofran® (Ondansetron), Reglan® (Metoclopramide), Compazine® (Prochlorperazine),
 Phenergan® (Promethazine), or any other medication for nausea/vomiting
- Other medications
- None

Check all that applies

36. Rate your overall satisfaction with your acute migraine treatment during your "study pregnancy", when 1 = Highly dissatisfied, 10 = Highly satisfied

Drop Down menu, with options 1-to-10 AND Not relevant (I did not use acute migraine treatment during my pregnancy)

37. Please mark all types of PREVENTIVE treatments (either pharmaceutical drugs and/or devices) you used for migraine during the "study pregnancy". Please include any treatment, even if used only once.

For each treatment type used, please indicate if you felt safe using it during the pregnancy by choosing the matching option of the dropdown menu.

- Amitriptyline, or any other generic tricyclic antidepressants
- Inderal[®] (Propranolol)
- Topiramate® (Topamax)
- Other generic oral preventive medication
- Nortriptyline (Pamelor), or any othernon-generic tricyclic antidepressants
- Botox® injection for migraine prevention (Botulinum toxin)Aimovig® (Erenumab),
 Ajovy® (Fremanezumab), Emgality® (galcanezumab-gnlm), Vyepti® (eptinezumabjjmr), that is any CGRP monoclonal antibodies (CGRP mAbs)
- Nurtec® ODT (Rimegepant)
- Devices (e.g., gammaCore, Cefaly)
- Other
- Did not use any preventive treatment
- 38. Rate your overall satisfaction with your PREVENTIVE migraine treatment during your "study pregnancy", when 1 = Highly dissatisfied, 10 = Highly satisfied

Drop Down menu, with options 1-to-10 AND Not relevant (I did not use preventive migraine treatment during my pregnancy)

TCH-011 Clinical Study Protocol

Doc ID: TECXXXX
Revision #: 1.0

Page: 23 of 25

- 39. Were you admitted to the emergency room (ER) or hospital for management/evaluation of headache during your "study pregnancy"?
 - Yes
 - No

Part 4 - Migraine postpartum

- 40. How many migraine days per month (on average) did you have in the 3 months postpartum after your "study pregnancy"?
 - Less than 4 days per month
 - 4-8 days per a month
 - 9-14 days per month
 - 15 days or more per month
- 41. Did you breast-feed during the first 3 months postpartum following your "study pregnancy"?
 - Yes
 - No

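### Secondary endpoint 7, a count of ER and urgent-care visits through 3 months postpartum, cannot be computed: the survey's only relevant item is a yes/no on ER or hospital admission for headache in pregnancy

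*Combined protocol and SAP*

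**What the plan says.** The Goal section states that the study will "assess the safety of treating migraine with Nerivio during pregnancy and 3 months postpartum". The Endpoints section adds: "Endpoints focus on the health of the mother and the baby, during pregnancy and three months postpartum". Item 7 of the secondary endpoints is "Visits to the emergency room or urgent care due to pregnancy and/or migraine symptoms during pregnancy and 3 months postpartum period (# of events", so its unit is a number of events.

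The data come from online forms: "The study is fully electronic, including an e-eligibility questionnaire, an e-ICF, and an e-survey". The eligibility message in Appendix 1 tells participants: "The questionnaire contains 52 questions".

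In Appendix 2, Part 3, Question 39 asks "Were you admitted to the emergency room (ER) or hospital for management/evaluation of headache during your" study pregnancy, with the answers yes and no. Part 4, on the postpartum period, has two questions. Question 40 begins "How many migraine days per month (on average) did you have in the" and refers to the first three postpartum months. Question 41 begins "Did you breast-feed during the first 3 months postpartum following your" and refers to the study pregnancy.

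**The concern.** The endpoint and the instrument do not describe the same quantity. If the survey runs as printed, the analyst will reach endpoint 7 with no variable that holds it. There are then two outcomes. A stated safety endpoint goes unreported, or the Question 39 result is reported under the endpoint 7 label. In the second case, a measure limited to headache and to pregnancy would be read as evidence on all pregnancy-related and migraine-related emergency care through the third postpartum month.

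**Working it through.** The plan gives no figure for endpoint 7. Its 114 per group is derived from gestational age and has no bearing here. The check is therefore a comparison of texts.

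**1. Is the questionnaire complete as printed?** Appendix 1 announces 52 questions, and items 1 to 52 all appear in Appendix 2. Questions 39 to 41 are intact. The gap does not come from lost text.

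**2. Which items could feed endpoint 7?** There are 12 screening + 52 survey = 64 numbered items. Those that touch on care or acute events are:
- Screening item 10: serious injury in pregnancy.
- Question 23: circumstances of delivery.
- Question 26: whether the baby went home with the mother.
- Question 39: the mother's ER or hospital admission for headache.
- Question 45: newborn complications.

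Only Question 39 concerns the mother's emergency care. Part 4 has no item on visits.

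**3. Endpoint and item side by side.**

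| Feature | Endpoint 7 | Question 39 |
|---|---|---|
| Unit | Number of visits | Yes/no |
| Setting | ER or urgent care | ER or hospital; urgent care not asked |
| Cause | Pregnancy and/or migraine symptoms | Headache; pregnancy-related visits not asked |
| Period | Pregnancy plus 3 months postpartum | Pregnancy only |

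This gives four shortfalls: count, urgent care, pregnancy-related cause and postpartum period. The item also merges in hospital admission, which the endpoint does not name.

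**4. Can endpoint 7 be recovered from the answer?** A *yes* does not say how many visits there were, and it does not separate an ER attendance from a hospital admission. A *no* is compatible with any number of urgent-care, pregnancy-related or postpartum visits. The count cannot be recovered, nor can an any-versus-none version of the full endpoint.

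**5. What does Question 39 give?** It gives, for each group, the proportion of women with any ER or hospital admission for headache during the study pregnancy.

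**6. What else covers the mother after delivery?** There are 1 primary + 7 secondary + 3 exploratory = 11 endpoints. Apart from endpoint 7, they concern the length or outcome of the pregnancy, the baby (including 3-month milestones), or the mother's ratings of acute treatment used in pregnancy. Endpoint 7 is the only one on the mother's own health postpartum.

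**The case against.** The strongest reply is that Question 39 is a reasonable working version of the endpoint. In everyday speech, being admitted to the ER for evaluation plausibly includes an ER visit without an overnight stay. A *no* would then mean no ER visit for headache during pregnancy. This much stands: Question 39 is informative, and one component is reportable in both groups. A reader might infer that the item is worthless, but the documents do not support that. They also do not make it the definition of endpoint 7. No text says so, and the two differ in unit, setting, cause and period.

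A second reply is that clinic records could supply the visits. None are described as a data source. The clinic contact mentioned at the end of Appendix 2 is to verify participation before payment.

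A third reply is that the postpartum period is covered elsewhere. This is partly right. A reader might infer that the whole postpartum part of the goal lacks data, which would be wrong, because secondary endpoint 6 (the baby's milestones at 3 months) is collected through Question 46. The gap concerns the mother only.

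Finally, the sponsor could redefine endpoint 7 to match Question 39. That would remove the contradiction before launch, but it would leave no endpoint on maternal health after delivery.

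**Conclusion.** The point holds. Endpoint 7 as defined cannot be computed from the planned survey. It falls short on four features, and what can be reported is a narrower proportion. One of 11 endpoints is affected, and with it the only endpoint data on the mother's own postpartum health.

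A reader might go further and infer that the study's main conclusion is compromised. The documents do not support this: the success criterion rests on gestational age alone, and that endpoint has its own items. The matter is worth correcting because a stated safety endpoint would otherwise go unreported or be mislabelled.

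The conclusion rests on two readings of the documents: that the forms in Appendices 1 and 2 are the complete instruments, and that no source beyond the electronic forms is used. It needs no numerical assumption.

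**What to change.** **Before launch.** Keep Question 39, since it is the only item on the mother's hospital admission for headache. Add two numeric items, each with a don't-know option, for the number of ER or urgent-care visits due to pregnancy and/or migraine symptoms:
- (i) during the study pregnancy;
- (ii) in the 3 months after the pregnancy ended. This wording also fixes the start of the period after a miscarriage or termination, which Question 21 allows.

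The items should say that each visit is counted once and that arrival for the delivery itself is not counted. The main reason (migraine, pregnancy-related, both) is asked only when the number is above 0. The question count given to participants in Appendix 1 must be updated.

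**If the survey has closed.** Report endpoint 7 as not assessed. Report Question 39 separately, as the proportion with an ER or hospital admission for headache during pregnancy, labelled as a substitute defined after data collection. State that visit counts, urgent-care visits, pregnancy-related visits and postpartum visits were not captured.

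**Cost.** The survey becomes slightly longer, and self-reported counts carry recall error. The survey date is not given. Eligible pregnancies may have begun as early as 1 November 2019, and screening accepts pregnancies that ended by 31 March 2022. If the survey starts no earlier than that later date, an assumption, visits early in the earliest pregnancies lie up to about 29 months back (November 2019 through March 2022), and further if it starts later. The counts should be reported with that limitation.

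### The primary comparison of two non-randomised groups recruited by different routes has no planned adjustment or balance check, although the survey collects pre-pregnancy confounders

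*Combined protocol and SAP*

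**What the plan says.** **Groups.** The design is a retrospective survey with a control group. In Study Design and Recruitment, "Study group participants will be recruited from Nerivio's user base", through in-app notification and/or email. Controls have never used the device and are referred by clinicians (headache and obstetric providers) acting as co-investigators. Both groups complete the same screening questionnaire.

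**Primary comparison.** Under Statistical Hypothesis: "In other words, the hypothesis is that the means of the two populations are equal". The test is two-sided at 0.05, and "If the null hypothesis is not rejected, the study will be deemed successful". Planned Sample Size assumes an SD of 2.7 weeks and a difference of 1.0 week, of which it says "This effect was selected as the smallest effect that would be important to detect". It gives 114 per group for 80% power and a 95% precision of plus or minus 0.70 weeks. It then adds: "Given this statistical requirement up to 400 participants will be recruited per group".

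**Analysis.** The section headed Statistical Analysis Plan contains four exclusion rules and nothing on estimation. No test, model, covariate, match, weight or baseline comparison is named there or elsewhere.

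**Control by restriction.** Both groups must be aged 18-42, with at least 4 migraine days per month before pregnancy and at least 4 attacks during it. Exclusions include "History of preterm birth (gestational age at deliver<37 weeks) in" earlier pregnancies, earlier birth defects, listed severe diseases, serious injury and multiple gestation. BMI of 40 or more is removed at analysis.

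**Data collected.** Part 1 of Appendix 2 records date of birth (Question 1), race/ethnicity (2-3), height and weight (4-5), comorbidities including high blood pressure and diabetes (6), smoking history (7), migraine days (8), preventive treatment (11) and prior pregnancies (15).

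**The concern.** Without randomisation, a difference in group means combines any device effect with whatever else separates the groups. People who own the device and answer the manufacturer's message may differ from people referred by a clinician. Restriction narrows the groups but does not balance what varies inside the limits: age within 18-42, BMI below 40, hypertension, diabetes, smoking history, prior pregnancies, migraine frequency above the threshold and preventive use.

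The verdict on the whole study rests on this one comparison. Bias in one direction can mask a real shortening of gestation, and under the plan's rule masking counts as success. Bias in the other direction can produce a difference that the device did not cause. A larger sample narrows the interval around the biased value and leaves the bias unchanged. The plan collects what it needs to deal with the measured part of the problem and gives it no role in the analysis.

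**Working it through.** **Inputs from Planned Sample Size:** SD 2.7, 114 per group, cap of 400 per group, difference 1.0 week, two-sided alpha 0.05.

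**Assumed inputs (not in the documents):** every bias value and every R² value below.

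**1. Reproducing the plan's figures.**
- n = 2 × [2.7 × (1.96 + 0.84)]² / 1.0² = 114.4 per group, against 114 stated.
- SE at 114 = 2.7 × √(2/114) = 0.358, which gives power of 79.8%.
- Precision = 1.96 × 0.358 = 0.70 weeks, as stated.

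The arithmetic is right for an unadjusted comparison of two means, so the fault is not in the sample-size calculation.

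**2. What a bias would do.** SE at 400 = 2.7 × √(2/400) = 0.191. With expected difference d = true effect + bias, P(reject) = Φ(d/SE − 1.96) + Φ(−d/SE − 1.96). The bias is taken to favour the device.

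| Assumed bias (weeks) | Power for true −1.0, n=114 | False rejection, true 0, n=114 | Power for true −1.0, n=400 | False rejection, true 0, n=400 |
|---|---|---|---|---|
| 0 | 79.9% | 5.0% | 99.95% | 5.0% |
| 0.075 | 73.5% | 5.5% | 99.8% | 6.8% |
| 0.15 | 66.2% | 7.0% | 99.4% | 12.3% |
| 0.2 | 60.9% | 8.7% | 98.7% | 18.2% |
| 0.23 | 57.7% | 9.9% | 98.1% | 22.6% |

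For scale, a binary factor that shifts gestational age by 1 week and differs in prevalence by 20 points gives 1 × 0.20 = 0.2 weeks. Four factors with effects of 0.8, 0.6, 0.5 and 0.4 weeks, each 10 points apart in the same direction, give 0.10 × 2.3 = 0.23 weeks.

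**3. Would a better success rule be enough?** Suppose success required the 95% CI of the crude difference to lie within 1.0 week. At a true 1.0-week shortening, false success should be 2.5%. With a 0.2-week bias it is 8.0% at n=114 and 18.1% at n=400. The success rule and the confounding are therefore separate faults.

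**4. Price of adjustment.** Adjustment multiplies the variance by about (1 − R² of outcome on covariates)/(1 − R² of group on covariates).

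| Assumed outcome R² / group R² | Factor | Power for 1.0 week, n=114 | n=400 |
|---|---|---|---|
| 10% / 10% | 1.00 | 79.9% | 99.9% |
| 5% / 20% | 1.19 | 72.8% | 99.8% |
| 0% / 30% | 1.43 | 64.8% | 99.2% |

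**The case against.** The strongest reply is that no error can be sized. Nothing in the documents shows that any covariate differs between the groups or how strongly it affects gestational age. That stands: the table in step 2 shows what a bias would do, not that one exists.

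Second, the plan already restricts both groups identically on several important risk factors and screens them with the same questionnaire. That also stands, and it makes large biases less plausible. By the arithmetic above, 0.5 weeks would need all four example factors to differ by about 22 points in one direction (0.5/2.3). Biases of that order are stress cases and are not relied on here. But restriction does not balance the factors left free to vary.

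Third, at the cap of 400 a bias of up to about 0.23 weeks hardly hides a 1.0-week shortening, because power stays at about 98% or more. There the main effect is false rejection, which makes the study fail. This is correct, but 400 is a maximum, and the masking figures apply if the analysed number is nearer 114.

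Fourth, adjustment cannot remove selection by recruitment route or unmeasured factors. That is true and limits what the fix can claim. It does not justify ignoring the measured factors or choosing covariates after the data are seen.

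**Conclusion.** The concern holds as a gap in the primary analysis. Followed as written, the plan yields a crude difference between two self-selected groups and lets it decide whether the study succeeded, while the measured confounders go unused. This matters enough to correct before analysis.

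The size is illustrative. With an assumed 0.2-week bias favouring the device, power for a true 1.0-week shortening falls from 80% to 61% and false rejection rises from 5% to 9% at 114 per group. At 400 per group the figures are about 99% and 18%. These rest on the plan's SD of 2.7, a normal approximation and a bias that the documents neither give nor rule out.

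Three stronger inferences are not supported. A reader might infer that the bias favours the device and hides harm; the documents do not show its direction. A reader might infer that confounding is wholly uncontrolled; the restrictions give partial control. A reader might infer that regression would make the comparison equivalent to a randomised one; it addresses measured factors only.

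**What to change.** **Primary estimate.** Specify the group difference in gestational age, with 95% CI and robust standard errors, from a linear regression on group plus pre-pregnancy covariates: age, BMI, race/ethnicity, hypertension, pre-pregnancy diabetes, smoking history, prior pregnancies, migraine days per month and preventive drug use. Take preventive drug use from Question 11 without its device options, which device users might tick. Fix the list and the handling of missing covariates before data are seen.

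**Leave out** items that arise during pregnancy (such as Questions 25 and 29-37) and items that nearly define the groups: Question 14, the device option in Question 10, and Question 9, whose count includes device use.

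**Add** a baseline balance table, keep the crude difference as a sensitivity analysis, and state that adjustment is partial and cannot remove selection by recruitment route or unmeasured factors.

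**Cost.** SAP wording and a modest extra analysis, with no new survey items. Precision may fall: over the assumed R² range, power is 80% to 65% at 114 per group and above 99% at 400. The stated power should be restated for the adjusted analysis. The cap leaves room, but the documents do not show that enough eligible device users exist.

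**Separately,** replace the rule that non-rejection means success, because any precision lost through adjustment would otherwise make success easier. One option is to require the CI to lie within the 1.0 week that the plan treats as the smallest important difference. That rule has its own cost. For 80% success with truly equal groups, the three R² scenarios need about 154, 182 and 219 analysed per group with a 95% CI, or about 125, 149 and 179 with a 90% CI. The choice of interval should be justified in its own right.

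### Success is defined as a non-significant difference test; at the proposed 114 per group, a true 1.0-week difference in gestational age would pass about 20% of the time

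*Combined protocol and SAP*

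**What the plan says.** All references are to the combined protocol and SAP.

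- **Endpoints, primary endpoint:** "Demonstrate that the study group is not different than the control group in regard to gestational age at delivery".
- **Data analysis, Statistical Hypothesis:** the study tests "the null hypothesis that treating with Nerivio during pregnancy does not impose a safety risk" relative to standard care. This is written as H0: GAt = GAc against H1: GAt ≠ GAc, two-tailed at 0.05. The decision rule is: "If the null hypothesis is not rejected, the study will be deemed successful".
- **Planned Sample Size:** 114 per group for 80% power with SD 2.7. On the effect size: "This computation assumes that the mean difference is less than 1.0 week", and then "This effect was selected as the smallest effect that would be important to detect". The section also expects to "report the mean difference with a precision (95% confidence level) of plus/minus 0.70 weeks", and ends: "Given this statistical requirement up to 400 participants will be recruited per group".
- **Statistical Analysis Plan:** some recruited women are left out of the analysis (for example BMI of 40 or more, or an LMP outside the window).
- **Endpoints, secondary endpoints:** introduced by "Demonstrate that the study group is not different from the control group in", with no test or success rule given.

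No equivalence or non-inferiority margin is stated, and the planned confidence interval has no part in the success rule.

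**The concern.** The hypotheses are the wrong way round for the aim. The absence of a safety problem is the null, so the study succeeds by default unless the data contradict it. A non-significant result can mean that the groups are alike, or that the data are too few or too variable to tell.

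The stated 80% power is therefore the chance that the study fails its own rule when the true difference is 1.0 week. The remaining 20% is the chance of declaring success in the presence of a difference that the protocol regards as important. Nothing fixes that error: it rises when fewer women are analysed or outcomes are more variable, and no minimum analysed number is tied to the rule.

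This is the primary criterion of a study of safety in pregnancy. A result labelled successful could be read as evidence of safety while its own confidence interval includes a shortening larger than the protocol's threshold.

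**Working it through.** **Inputs**, from Statistical Hypothesis and Planned Sample Size: n = 114 per group, SD = 2.7 weeks, two-sided alpha 0.05, difference 1.0 week.

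**1. Reproduce the plan's figures.**

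- SE = 2.7 × √(2/114) = 0.3576 weeks.
- Normal approximation: power = Φ(1.0/0.3576 − 1.96) = Φ(0.836) = 79.8%. Noncentral t with 226 df: 79.5%. The stated 80% is confirmed.
- 95% half-width = 1.96 × 0.3576 = 0.701, or 1.9705 × 0.3576 = 0.705 with t. The stated ±0.70 is confirmed.
- These figures hold at a difference of exactly 1.0 week. Power is lower for smaller differences, so describing the assumption as a difference below 1.0 week reverses it.

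**2. Probability of success under the rule.** P(success) = 1 − power of the two-sided test. At 114 per group and a true 1.0 week it is 1 − 0.795 = 20.5% (20.2% by the normal approximation). At 0.7 week it is 50%, at 0.5 week 71%.

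**3. What a success can contain.** The largest non-significant observed difference equals the half-width, so the furthest 95% limit is twice that: 2 × 0.705 = 1.41 weeks at 114 per group.

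**4. Dependence on analysed n** (SD 2.7, noncentral t):

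| Analysed n per group | Furthest 95% limit with success (weeks) | P(success), true 1.0 week | P(success), true 0.5 week |
|---|---|---|---|
| 57 | 2.00 | 50% | 83% |
| 100 | 1.51 | 26% | 74% |
| 114 | 1.41 | 20.5% | 71% |
| 200 | 1.06 | 4.1% | 54% |
| 226 | 0.998 | 2.4% | 50% |
| 400 | 0.75 | 0.05% | 26% |

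Fewer data make success easier. At 400 the opposite fault appears: a true 0.5-week difference, half the protocol's threshold, fails 74% of the time.

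**5. Dependence on SD.** With assumed larger SDs, P(success) at 114 per group and a true 1.0 week is 29% (SD 3.0) or 43% (SD 3.5).

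**6. Interval-against-margin rules**, with an assumed margin of 1.0 week, a two-sided 95% interval and SD 2.7:

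| Rule | True difference | Power at 114 | n per group for 80% | Power at 400 |
|---|---|---|---|---|
| Non-inferiority | 0 | 79.5% | 116 | 99.95% |
| Non-inferiority | −0.2 week | 61% | 180 | 98.7% |
| Equivalence | 0 | 59% | 155 | 99.9% |
| Equivalence | 0.2 week | not computed | 185 | 98.7% |

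Non-inferiority power is from the noncentral t. Equivalence power integrates over the distribution of the pooled variance.

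**The case against.** - **The 20% is not hidden.** It is the complement of the power the protocol states. That is true; the fault lies in reading non-rejection as success.
- **The consequence depends on n.** From 226 analysed per group, if the observed SD is 2.7, every success has a 95% interval inside ±1.0 week, and the present rule is then stricter than an equivalence test at that margin. This is correct, and it is why the 20% is tied to 114. But 114 is the proposed size, 400 is only a ceiling, and the rule requires no minimum.
- **Sizes below 114 were not proposed.** A fair reading is 114 analysed, with over-recruitment to cover exclusions. The rows for 57 and 100 illustrate the direction of the error only.
- **A margin rule does not fix the error at exactly 2.5%.** It does so for non-inferiority. For equivalence 2.5% is an upper bound (0.6% at 57 per group). In both cases it covers sampling error only: the groups are not randomised and are recruited by different routes, and no interval rule removes bias.
- **Equivalence could use a 90% interval** (5% on each side). That needs about 126 per group, with 75% power at 114. It is a legitimate alternative that accepts a higher error at the margin.
- **The remedy is sensitive to SD too.** At SD 3.0 or 3.5, non-inferiority needs 143 or 194 per group, and equivalence 191 or 259.
- **The secondary endpoints are a matter of wording.** With no test, rule or event rates in the plan, any power figure for them rests on assumptions, and the conclusion does not depend on one.

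None of this supports non-rejection as proof of no difference.

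**Conclusion.** The concern holds. The success rule cannot deliver the stated aim. At the proposed 114 per group it would pass a true 1.0-week difference, in either direction, about 20% of the time. This rests on the protocol's SD of 2.7, equal groups, 114 women analysed in each and no bias; a larger SD or fewer analysed women raises the figure, and more women lower it.

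The reversed description of the 1.0-week assumption is a drafting slip, since the arithmetic shows that 1.0 was used. For the secondary endpoints the fault is limited to a promise to demonstrate no difference, which a non-significant result could not keep.

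**What to change.** 1. **Delete the non-rejection rule.** Base success on the two-sided 95% confidence interval for GAt − GAc against a margin that the sponsor states and justifies. The protocol's 1.0 week is the natural candidate, but the protocol does not call it an acceptable loss, so the justification has to be written.
2. **Choose one set of hypotheses.**
   - *Non-inferiority*, if only shorter gestation is the safety concern: H0: GAt − GAc ≤ −1.0 week; H1: GAt − GAc > −1.0 week; success if the lower limit is above −1.0.
   - *Equivalence*, if a two-sided claim is meant literally: H0: |GAt − GAc| ≥ 1.0 week; H1: |GAt − GAc| < 1.0 week; success if the whole interval lies within ±1.0.
3. **Rewrite the power statement to match**, giving the SD, the assumed true difference and the *analysed* number per group. At SD 2.7, non-inferiority needs 116 (180 if the true difference is −0.2 week) and equivalence needs 155 (185 if it is 0.2 week). Show the sizes for a larger SD as well.
4. **Reword the secondary endpoints** as estimates of the group difference with 95% confidence intervals, exact for rare events, and state that p > 0.05 will not be read as no difference.

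**Cost:** protocol and SAP wording plus a short margin justification, settled before the data are analysed. Non-inferiority needs essentially the planned size, though 114 per group gives only 61% power if the true shortening is 0.2 week. Equivalence needs 155 − 114 = 41 more analysed women per group. All these sizes are below the ceiling of 400 recruited per group, with room for exclusions.
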